All safety analyses will be conducted using the Safety Analysis Set. No inferential tests of safety data will be performed. Descriptive summaries of safety data will be presented. Adverse events (treatment-emergent unless otherwise specified) will be presented by system organ class (SOC) and preferred term (PT) for each treatment group.

Discontinuations and Data Handling Rules

The analysis for the primary efficacy endpoint as well as for the continuous key secondary efficacy endpoints will handle missing values using a CR-imputed data set generated from the multiple imputation approach described for the primary efficacy endpoint. For all responder analyses, patients who discontinue for any reason will be considered as non-responders from the time of discontinuation onwards. No pooling of sites is planned for the efficacy analyses.

Number of patients (planned):

Approximately 108 patients are planned to be randomized into the trial 1:1:1.

[figure not shown]

Figure 1: Trial Design

Table 1: Schedule of Assessments

Phase	Screening	Run in: PS optimization phase	Run-in: PS stabilization phase	Treatment phase								EOT	FU ¹⁹	
				D1 ¹⁸	D3	D8	D15	D29	D57	D85	D113	D141		
Visit day or week	up to 14 d prior to Op1	Duration: 2 to 4 weeks \pm 4d*	Duration: 2 to 4 weeks \pm 4d*	\pm 1	\pm 2 (W1)	\pm 3 (W2)	\pm 5 (W4)	\pm 5 (W8)	\pm 5 (W12)	\pm 5 (W16)	\pm 7 (W20)	\pm 7 (W24)	D197 \pm 7 (W28)	
Visit #	Sc	Op1, Op2 etc.	St1, St2 etc.	V1	V2	V3	V4	V5	V6	V7	V8	V9	V10	FU
Visit type (site, phone)	S	S	S	S	P	S	S	S	S	S	S	S	S	S
Informed consent	X ¹													
Inclusion/exclusion criteria	X			X										
Demographics (age, gender, race and ethnicity [if allowed in the participating country])														
Medical history and concomitant illness	X ²													
SBS characteristics	X													
PS regimen (day, volume, and content) ³	X	X	X	X	X	X	X	X	X	X	X	X	X	
Definition of individual drinking menu (volume, content & timing) ⁴	X	X	X	X	X	X	X	X	X	X	X	X	X	
Body weight/height (height at Sc only) ⁵	X	X	X	X	X	X	X	X	X	X	X	X	X	
Concomitant medications/procedures	X	X	X	X	X	X	X	X	X	X	X	X	X	
ECG	X			X										X
Vital signs (heart rate, blood pressure, body temp)	X	X	X	X	X	X	X	X	X	X	X	X	X	
Adverse Events		X	X	X	X	X	X	X	X	X	X	X	X	
Physical examination (Full PE at Sc; SBS symptom-driven at all other visits)		X (full)		X	X	X	X	X	X	X	X	X	X	
Colonoscopy	X ⁶													
Laboratory														
Urine sample ⁷	X	X	X	X	X	X	X	X	X	X	X	X	X	

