The Copy Reference (CR) and Jump to Reference (J2R) approaches multiply impute missing data using estimated means in the control group. This is justifiable scientifically under the assumption that patients who stop taking the therapy will no longer benefit from it in the future, and thus will tend to have outcomes similar to those in the control group. The difference in the two methods is that the Copy Reference approach presumes patients who withdraw from the active arm were on the control (rather than the active) treatment before dropout; the resulting positive residuals before withdrawal leads to imputed values that slowly (rather than quickly) trend toward the estimated mean on the control arm. The Copy Reference is used in the primary analysis and the Jump to Reference will be applied as a sensitivity analysis. As a second sensitivity analysis, the Copy Increments from Reference will be used. This scenario provides a contrast to the extreme effect of J2R by assuming that in the future a dropout continues from their established position, but the subsequent changes in mean profile follow that of the reference arm.

For all binary responder analyses, patients who discontinue for any reason will be considered as non-responders from the time of discontinuation onwards.

Imputation rules for the handling of missing data for PROs and health economic assessments will be described in the SAP.

No pooling of sites is planned for the efficacy analyses.

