3.2. KEY SECONDARY EFFICACY ENDPOINTS

The following 4 key secondary efficacy endpoints will be analyzed to assess the treatment effect using the FAS. The key secondary endpoints will be derived based on the actual weekly PS volume or the number of days on actual PS a week, using the selected valid 7-day period at Week 12, 20, and 24, respectively. For details on the derivation see Appendix A.

First key secondary efficacy endpoint: Clinical response, defined as at least 20% reduction in actual weekly PS volume from baseline to both Weeks 20 and 24

The primary estimand will handle the intercurrent event of treatment discontinuation under a 'composite strategy', i.e. incorporating the intercurrent event in the response definition. For patients who discontinue treatment prematurely, a non-response will be imputed, indicating failure to randomized treatment. This assesses the treatment effect of

• Difference in percentage of clinical response without treatment discontinuation between glepaglutide treatment group and placebo in the SBS population.

Missing data for other reasons will be imputed with a non-response.

The difference in clinical response rates between each glepaglutide group and the placebo will be calculated using Mantel-Haenszel weighing and presented with 95% confidence intervals (using the Wald estimation method). Whether the difference equals zero will be tested using the Cochran-Mantel-Haenszel (CMH) adjusted for the stratification factor. In the presence of strata with zero counts in the crosstabulation between stratification factor and treatment, an unadjusted difference in clinical response rates between each glepaglutide group and the placebo will be calculated (i.e. without stratification), to avoid inappropriate weighing of the risk differences in each stratum. The null hypothesis of a difference equals zero will still be tested using the Cochran-Mantel-Haenszel (CMH), with a single contingency table.

As a sensitivity analysis of the primary estimand of first key secondary efficacy endpoint, the actual weekly PS volume will be derived using a valid 14-day period prior to the visit. For details on the derivation of actual weekly PS volume within a 14-day period, see Appendix A. Handling of missing data and analysis of this endpoint will follow that of the primary estimand of first key secondary efficacy endpoint.

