Reduction of at least 30% in actual weekly PS volume from baseline to both Weeks 20 and 24

The difference in response in reduction of $\geq 30\%$ in PS volume from baseline to both Weeks 20 and 24 between each glepaglutide treatment group comparison to placebo will be tested using the CMH test adjusted for the stratification factor will be analyzed in a similar manner as the clinical response endpoint (first key secondary endpoint).

Reduction in prescribed weekly PS volume of 100% (weaned off) at Week 24

The difference in response in prescribed weekly PS volume of 100% (weaned off) at Week 24 between each glepaglutide treatment group comparison to placebo will be tested using the CMH test adjusted for the stratification factor will be analyzed in a similar manner as the weaned off endpoint based on actual PS volume (fourth key secondary endpoint).

PGIC improvement at weeks 4, 12, 20, and 24

PGIC improvement is defined as responding "Very Much Improved" or "Much Improved" on a 7-point Likert Scale for each of the weeks 4, 12, 20, and 24. Improvement between each glepaglutide treatment regimen compared to placebo will be tested by week, using the CMH test adjusted for the stratification factor. In similar fashion, improvement between each glepaglutide treatment regimen versus placebo will be tested using collapsed categories of Improvement, No Change, and Worsening, where Improvement is defined as a response of "Very Much Improved" or "Much Improved" or "Minimally Improved", and No Change is defined as the response of "No Change", and Worsening is defined as a response of "Minimally Worse" or "Much Worse" or "Very Much Worse". Improvement using collapsed 25 August 2022 Confidential Page 24 of 65

categories between each glepaglutide treatment regimen compared to placebo will tested by week using a Mantel-Haenszel chi-squared test for ordered categories. No imputation for missing values will be performed.

Change in weight from baseline to Week 24

The change in body weight (kg) from baseline to Week 24 will be presented descriptively by baseline BMI subgroup. Descriptive statistics will include the number of non-missing observations, mean, SD, median, minimum, and maximum values. A shift table by BMI subgroup from baseline to Week 24 will be presented. The BMI subgroups are defined as: <18.5 kg/m2, \geq 18.5 to <25 kg/m2, \geq 25 to <30 kg/m2 and \geq 30 kg/m2.

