5.3. MISSING DATA AND DATA HANDLING RULES

Every effort will be made to collect all data at specified time points, according to the schedule of trial events. Reasons for withdrawal from the trial will be recorded on the eCRF.

For actual weekly PS volume, a detailed algorithm is included in Appendix A. In brief, for each visit, the actual weekly PS volume will be derived by using a valid 7-day period closest to the visit where

1. the actual weekly PS volume accounted for \geq 90% of prescribed weekly PS volume

or

2. there is at least one actual PS volume accounted for by the patient in the eDiary for each day in the valid 7-day period

For all post-baseline visits, the 7-day period is allowed to start up to 14 days before a visit, provided that it does not start before the previous visit. For baseline visits, the 7-day period is allowed to start up to 30 days before the baseline visit, provided that it does not start before the latest optimization visit. The Day 3 and Week 1 visits are not included in the calculations.

Note that, if the last PS prescription during the treatment period has been stopped more than 7 days prior to a visit, and there are no entries of actual PS volumes recorded by the patient in the eDiary within 7-days prior to this visit then the actual weekly PS volume will be set to zero.

The efficacy endpoints will be missing at visits, where no valid 7-days period can be found based on the above algorithm.

Any missing data during the trial prior to trial completion or discontinuation will remain as missing at that time point. However, several multiple imputation methods will be used to impute missing data for the primary efficacy endpoint as well as for the key secondary efficacy endpoints. See 5.3.1 for details of the multiple imputation method.

Imputation rules for the handling of missing data for PROs and health economic assessments will follow rules per each assessment manual.

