5.3.2. Patient Reported Outcomes

The PGIC, SBS-I and EQ-5D-5L PROs will be used to investigate the effects of treatment on health-related quality of life. There are three questionnaires:

- 1. The Patient Global Impression of Change (PGIC) is a one item outcome measure on a 7-point scale ordered from 'Very much worse' to 'Very much improved'.
- 2. The SBS-I scale assesses the symptoms and impact of SBS on everyday life and comprises 8 items, where responses to the individual items are registered on a numerical rating scale from 0=Not at all to 10=worst possible. By design, only integer responses are allowed. However, for existing recordings (3 instances), scores which are recorded in half increment values and entered into the database as such will be rounded to the higher response value for analysis purposes.
- 3. The EQ-5D-5L is a standardized measure of health status developed by the EuroQol Group and comprises 5 items, each on a 5-point scale, plus a general health item using a VAS scale 0-100.

Questionnaires must be completed at site visits prior to any other trial related assessment. The PGIC must be completed first, followed by the SBS-I, and then the EQ-5D-5L. The SBS-I and EQ-5D-5L are to be completed once during PS optimization phase, at the start of and after the stabilization phase, and all PROs are to be completed during treatment as indicated in the Schedule of Assessments.

An overall summary table of the number and percentage of subjects who provided each type of questionnaire data will be presented by treatment group. Percentages presented in subsequent

25 August 2022

tabular summaries for each type of questionnaire will be based on the number of subjects who provided respective questionnaire data.

All questionnaires will be analyzed per item descriptively by treatment group and by SBS Anatomy Group. Summaries will be presented by domain as defined within each questionnaire. Presentations will focus on the 12 and 24-week time points.

The association between PGIC and the percentage change from baseline in PS volume at 12 and 24 weeks will be evaluated. Association between percentage improvement in PS volume and PGIC data (categorical data) for all treatment groups combined will be assessed using the Spearman rank-order and Kendall's tau-b correlation coefficients. Graphical methods will be applied as applicable.

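### Binary PGIC improvement is tested on observed cases, while the protocol counts discontinued patients as non-responders in all binary responder analyses; the SAP neither exempts PGIC nor explains the difference

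*SAP*

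**What the plan says.** **PGIC in the SAP.** Section 3.4 defines improvement as one of the two best categories on the 7-point scale. Each regimen is compared with placebo, and improvement "will be tested by week, using the CMH test adjusted for the stratification factor". A second test uses three ordered categories. The paragraph then ends: "No imputation for missing values will be performed". Section 5.3.2 adds that percentages in "tabular summaries for each type of questionnaire will be based on the number of subjects who provided respective questionnaire data", and Section 5.1 makes non-missing observations the default denominator.

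**The responder rule in the protocol.** Section 12.6: "For all binary responder analyses, patients who discontinue for any reason will be considered as non-responders from the time of discontinuation onwards". The synopsis is equally broad: "For all responder analyses, patients who discontinue for any reason will be considered as non-responders from the time of discontinuation onwards".

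**Other binary endpoints in the SAP.** Section 3.2, for the binary key secondary endpoints: "For patients who discontinue treatment prematurely, a non-response will be imputed, indicating failure to randomized treatment". Data missing for other reasons are also set to non-response (Table 6). The 20%, 30%, 40% and prescribed weaned-off endpoints in Section 3.4, and the endpoints of at least 2 and at least 3 fewer PS days in Section 3.5, are analysed in the same way.

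**Rules for PROs.** Protocol Section 12.6, just after the responder rule: "Imputation rules for the handling of missing data for PROs and health economic assessments will be described in the SAP". SAP Section 5.3: "Imputation rules for the handling of missing data for PROs and health economic assessments will follow rules per each assessment manual".

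**Declared changes.** SAP Section 8 has no row on PGIC or on the responder rule. The version log in SAP Section 9 mentions PGIC only for category collapsing and correlation coefficients.

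**The concern.** PGIC improvement is a two-category response tested by CMH, so the protocol's wording covers it. It is the only binary responder endpoint in the SAP that does not follow non-response. A programmer has three candidate rules: non-response after discontinuation (protocol), no imputation (SAP 3.4) and the assessment manuals (SAP 5.3).

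The rules answer different questions. Under non-response every randomized and treated patient stays in the denominator, and stopping counts as failure. On observed cases the denominator is whoever filled in the questionnaire at that visit. If missingness differs by arm and relates to outcome, that comparison no longer follows randomization. At about 36 patients per arm, a few missing questionnaires can move a nominal p-value across 0.05. PGIC reports the patient's own view of benefit and will be read that way even though it is not a confirmatory endpoint.

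**Working it through.** **1. The plan's own figure.** The documents give no power, response rate or missing-data rate for PGIC. The nearest stated figure is 95% power at N=108 for either regimen on the primary endpoint (Protocol 12.7, SAP 2.6). With SD 2.62, 36 per arm, differences of 2.2 and 2.0 L/week and two-sided alpha 0.025, the normal approximation gives 90.7% and 84.1% for the single comparisons. With correlation 0.5 from the shared placebo arm, power for at least one is 95.8%. The stated figure reproduces to within a point, and nothing in it depends on PGIC.

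**2. How the two rules differ.** Let pA and pP be the response rates among observed patients and dA and dP the fractions missing.

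- Observed-case difference: pA − pP
- Non-response difference: pA(1 − dA) − pP(1 − dP)
- Observed-case minus non-response: pA·dA − pP·dP

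The sign depends on pA·dA against pP·dP. With pA = 0.50 and pP = 0.25 (assumed), the observed-case difference is 25 points:

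| Missing, active / placebo (assumed) | pA·dA − pP·dP | Non-response difference |
|---|---|---|
| 5% / 5% | 0.0250 − 0.0125 = +1.3 points | 23.8 |
| 10% / 10% | 0.0500 − 0.0250 = +2.5 | 22.5 |
| 15% / 5% | 0.0750 − 0.0125 = +6.3 | 18.8 |
| 20% / 5% | 0.1000 − 0.0125 = +8.8 | 16.3 |
| 5% / 15% | 0.0250 − 0.0375 = −1.3 | 26.3 |

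**3. Whole-patient examples, 36 per arm.** Assumed: 16 responders on active, 9 on placebo, and every missing patient discontinued without a later PGIC. The test is the Mantel-Haenszel chi-square on one 2×2 table, without strata: Q = (a − E)²/V, where E = n1·m/N, V = n1·n0·m·(N − m)/[N²(N − 1)], a is the number of active responders, m all responders, n1 and n0 the arm sizes, and N = n1 + n0.

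| Missing, active / placebo | Observed cases | Difference, p | Non-response | Difference, p |
|---|---|---|---|---|
| 4 / 1 | 16/32 vs 9/35 | 24.3 points, 0.042 | 16/36 vs 9/36 | 19.4 points, 0.085 |
| 1 / 1 | 16/35 vs 9/35 | 20.0 points, 0.083 | 16/36 vs 9/36 | 19.4 points, 0.085 |
| 1 / 4 | 16/35 vs 9/32 | 17.6 points, 0.14 | 16/36 vs 9/36 | 19.4 points, 0.085 |

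First row, observed cases: E = 32·25/67 = 11.94, V = 3.969, Q = 4.15. Non-response: E = 12.5, V = 4.137, Q = 2.96.

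**4. What the examples leave out.** They cover missing questionnaires only. Protocol Sections 7.5 and 7.6 keep patients who stop treatment in the visit schedule, so some will have a PGIC recorded after stopping. The SAP uses those values as observed. The protocol rule, read as treatment discontinuation (the reading SAP 3.2 uses), would count them as non-response.

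**The case against.** The best defence is delegation. The sentence after the responder rule in Protocol Section 12.6 leaves missing-data rules for PROs to the SAP, PGIC is one of the three PROs, and Protocol Section 12.1 makes the SAP the overriding document. Protocol Section 12.3.4 sets no missing-data rule for PGIC, whereas Section 12.3.2 sets one for each binary key secondary endpoint. This much stands: the SAP may set the rule. A reader might infer an undeclared departure from the protocol, but the documents do not clearly support that charge. What delegation does not settle is a PGIC value observed after discontinuation, which is not missing data, or which of the SAP's own two PRO rules applies.

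The reach of the quoted sentence is also open. It follows the ordered-category test, so applying it to the binary test is an inference from position. SAP Sections 5.1 and 5.3.2 support the inference, and the SAP gives the binary test no other specific rule.

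Three stronger readings are tempting and fail:

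- **That the analysis is restricted to completers.** It is not. Testing is by visit and uses everyone with a PGIC at that visit, including patients who have stopped treatment.
- **That observed cases inflate the drug effect.** They can, but the 1 / 4 example shows the reverse. The protocol expects few discontinuations on active treatment and gives no rates.
- **That the clinical-meaningfulness case is affected.** The anchor analyses in SAP Section 3.1.1 pool all treatment groups and relate PS change to PGIC category. They do not use the by-arm test.

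Finally, counting an observed favourable report as failure is a composite estimand. It is a legitimate choice, but not the only one.

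**Conclusion.** The inconsistency is real and worth correcting, but its consequences are limited. The protocol's rule covers all binary responder analyses, the SAP's other binary responder endpoints follow non-response, and PGIC improvement is left on observed cases with no stated exemption and no explanation in SAP Section 8. SAP Sections 3.4 and 5.3 also give different rules for missing PRO data.

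The direction is not determined. In the assumed whole-patient examples the observed-case difference runs from 4.8 points above the non-response difference to 1.9 points below it. In the assumed rate scenarios it runs from 8.8 above to 1.3 below. These sizes rest on assumed response and missing-data rates, an unstratified test and 36 per arm.

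PGIC is a secondary endpoint outside the gatekeeping and unadjusted for multiplicity (SAP 3.4), so no confirmatory claim depends on this point.

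**What to change.** In SAP Section 3.4, replace the closing sentence on PGIC with text to this effect:

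*For the binary PGIC improvement test, patients who discontinued are counted as not improved from discontinuation onwards, in line with Protocol Section 12.6. PGIC values missing for other reasons are counted as not improved, as for the other binary endpoints. An observed-case analysis is supportive. The ordered three-category test uses observed data.*

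The second sentence goes beyond the protocol rule, which covers discontinuation only. It follows the SAP's handling of its other binary endpoints.

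Amend SAP Section 5.3 so that its reference to assessment manuals does not conflict with Section 3.4 for PGIC. If the sponsor prefers observed cases for the main PGIC test, it should say in Section 3.4 that PGIC is exempt from the discontinuation rule and give the reason in Section 8.

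The cost is a few sentences and one supportive table. The reported response rates will be somewhat lower, and PGIC reports given after discontinuation will count only in the supportive analysis.

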7.2 Inclusion Criteria

The patient must meet all of the following inclusion criteria:

1. Informed consent obtained before any trial-related activity.
2. Age ≥ 18 years and ≤ 90 years at Screening.
3. Diagnosis of SBS defined as remaining small bowel in continuity of estimated less than 200 cm [equal to 79 inches] and with the latest intestinal resection being at least 6 months prior to Screening and considered stable with regard to PS need. No restorative surgery planned in the trial period.
4. Requiring PS at least 3 days per week.
5. Willing to adhere to an individual pre-defined drinking menu during 48-hours measuring intervals.
6. Willing to maintain a stable weight ($\pm 5\%$) for the duration of the trial (24 weeks).
7. Having:
 - a. A stoma Or
 - b. Colon-in-Continuity (CiC) with documented colonoscopy performed during Screening and which does not give rise to any safety concerns.
1. Note: A colonoscopy performed within 6 months prior to Screening and not giving rise to any safety concerns is accepted. For patients with a remnant colon, which is not connected to the passage of foods and is thereby dormant, a computerized

tomography (CT) scan or magnetic resonance imaging (MRI) (if standard of care at site) will suffice at the discretion of the investigator.

8. Having a) a stoma Or b) colon-in-continuity (CiC) and able to separate stool and urine during the 48 hours measuring intervals.

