11.3.3 Weight and Height

Body weight (kg or lb) will be measured at Screening, during the Optimization and Stabilization Phases, and at every trial visit (except Visit 2-phone assessment). During weight measurements patients should wear light clothing and no shoes. Stoma bags should be emptied prior to the measurement. At Screening Visit height (cm or inches) will be measured and the patient's body mass index (BMI) will be calculated.

Patients should be encouraged to measure their body weight at home weekly to detect potential signs of fluid retention early (before edema becomes readily visible). If the weight changes, patients should be instructed to call the trial site for guidance.

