12.1 General Considerations for Data Analysis

This is a multicenter, placebo-controlled, randomized, parallel-group, double-blind, fixed-dose, Phase 3 trial to demonstrate the superiority of glepaglutide 10 mg given twice weekly and once weekly SC versus placebo in stable SBS patients.

A detailed Statistical Analysis Plan (SAP) will be written specifying all analyses that will be performed and completed prior to database lock and analysis. The SAP will contain any modifications to the analysis plan described below, and thus serves as the overriding document dictating the statistical analyses to be performed. Any changes from the SAP will be explained in the Clinical Trial Report (CTR).

In general, all data will be summarized with descriptive statistics for each treatment group. Unless otherwise specified, continuous data will be summarized by presenting the number of

non-missing observations, mean, standard deviation (SD), median, minimum, and maximum. Categorical data will be summarized by presenting the number of patients and percentage for each category.

Baseline is defined as Visit 1 (Day 1) for efficacy analyses, and defined as the last available value prior to or on Visit 1 (Day 1) for safety analyses.

Inferential statistical analyses of the primary and secondary efficacy endpoints will be performed as described below. All comparisons will be between each ZP1848-17111 treatment group and placebo. Listings of individual patient data will be presented.

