PGIC improvement is defined as responding “Much improved” or “Very much improved” on a 7-point Likert Scale for each of the weeks 4, 12, 20, and 24. Improvement between each glepaglutide treatment regimen compared to placebo will be tested using the CMH test with stratification on the randomization stratification factor.

Change in weight from baseline to Week 24

The change in body weight (kg) from baseline to Week 24 will be presented descriptively in patients who are (1) below ideal weight at the start of the treatment period ($BMI < 18.5 \text{ kg/m}^2$ at baseline), and (2) maintaining an ideal/acceptable weight at the start of the treatment period ($18 \leq BMI \leq 25 \text{ kg/m}^2$ at baseline). The change in body weight (kg) from baseline to Week 24 will also be categorized into three groups of less than 5% change, 5% to 10% change, and greater than 10% change. In addition will the proportion of patients in each treatment group who are either underweight ($BMI < 18.5 \text{ kg/m}^2$), normal weight ($18.5 \leq BMI \leq 25 \text{ kg/m}^2$), or overweight ($BMI > 25 \text{ kg/m}^2$) will be presented descriptively in patients who are (1) below ideal weight at the start of the treatment period ($BMI < 18.5 \text{ kg/m}^2$ at baseline), and (2) maintaining an ideal/acceptable weight at the start of the treatment period ($18 \leq BMI \leq 25 \text{ kg/m}^2$ at baseline). Descriptive statistics will include the number of non-missing observations, mean, SD, median, minimum, and maximum values.

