The change in body weight (kg) from baseline to Week 24 will also be presented by three groups: less than 5% change, 5% to 10% change, and greater than 10% change.

Prescribed weekly PS volume

The prescribed weekly PS volume at baseline, Weeks 1, 2, 4, 8, 12, 16, 20, and 24 will be defined as the prescribed weekly PS volume received during the 7-day period prior to these visits.

The source for the derivation will be the prescribed PS volume information recorded in the eCRF by the investigator; for details on the derivation see Appendix A.

The change in prescribed weekly PS volume from baseline to Week 24 will be analyzed with the same statistical methodology as for the primary analysis of the primary endpoint.

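### The weight-change bands carry no sign, so no planned summary counts patients per arm who lost 5–10% or more than 10% separately from those who gained it

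*SAP*

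**What the plan says.** Protocol 12.3.4 says that the Week 24 change in body weight will be "categorized into three groups of less than 5% change, 5% to 10% change, and greater than 10% change". SAP 3.4 keeps the bands: "less than 5% change, 5% to 10% change, and greater than 10% change". Neither text says whether the percentages are absolute or signed. The SAP sentence also leaves open whether the output is a count of patients per band or statistics on the kg change within each band.

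The same SAP endpoint has two further outputs:

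- The first concerns the change in kg: "The change in body weight (kg) from baseline to Week 24 will be presented descriptively by baseline BMI subgroup". The statistics are the number of observed values, the mean with its SD, the median and the two extremes.
- The second concerns movement between BMI classes: "A shift table by BMI subgroup from baseline to Week 24 will be presented". The classes are below 18.5, 18.5 to below 25, 25 to below 30, and 30 kg/m² or more.

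The weight paragraph does not itself mention treatment arms. Presentation by arm follows from the general rule in Protocol 12.1 that "all data will be summarized with descriptive statistics for each treatment group".

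**The concern.** The trial reduces parenteral fluid and nutrition, so a loss of weight and a gain of weight mean different things. Protocol 11.3.3 encourages weekly weighing at home "to detect potential signs of fluid retention early", and inclusion criterion 6 (Protocol 7.2) asks that patients be "Willing to maintain a stable weight" within ±5%. A reader of the trial report will want to know how many patients in each arm fell below that range and how many rose above it. Bands without a sign do not answer this.

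Little else in the SAP fills the gap. Protocol 11.3.1 lists weight as a safety parameter, but the SAP safety list (3.6) and its vital signs section (7.4) omit it. SAP 3.4 is the only SAP section that summarises change in weight.

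**Working it through.** The plan states no figure for this table, so there is nothing to reproduce. The checks below ask what the planned outputs can and cannot show. The 36 patients per arm come from Protocol 6.1. All weight-change values are assumptions for illustration, because the documents give none.

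**1. The band table alone.** Suppose percentage change is normal with mean m and SD s. Then:

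- share below 5% = Φ((5 − m)/s) − Φ((−5 − m)/s)
- share above 10% = Φ((−10 − m)/s) + 1 − Φ((10 − m)/s)
- the remainder is the 5–10% band.

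With s = 5 and m = −4, the first share is Φ(1.8) − Φ(−0.2) = 54.3%, the second is Φ(−1.2) + 1 − Φ(2.8) = 11.8%, and the remainder is 33.9%. By symmetry, m = +4 gives the same row.

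| Assumed SD (points) | Mean −4% or +4%: <5 / 5–10 / >10 | Mean −2% or +2%: <5 / 5–10 / >10 |
|---|---|---|
| 4 | 58.6 / 34.6 / 6.7% | 73.3 / 24.3 / 2.4% |
| 5 | 54.3 / 33.9 / 11.8% | 64.5 / 29.2 / 6.3% |
| 6 | 49.9 / 33.2 / 16.8% | 57.0 / 31.6 / 11.4% |

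Five signed bands separate the arms. With SD 5, in the order loss >10, loss 5–10, within ±5, gain 5–10, gain >10:

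- mean −4%: 11.5 / 30.6 / 54.3 / 3.3 / 0.3%
- mean +4%: 0.3 / 3.3 / 54.3 / 30.6 / 11.5%

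In this illustration the planned mean change in kg would also differ in sign between the arms. The band table fails here, but the endpoint as a whole does not.

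**2. The BMI shift table.** A patient at BMI 21 leaves the 18.5 to below 25 class only after a loss of more than 1 − 18.5/21 = 11.9% or a gain of 25/21 − 1 = 19.0%. The table shows direction, but too coarsely to replace bands at 5% and 10%.

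**3. All planned weight outputs together.** This example was built to test them and is not a forecast. Take 36 patients per arm with equal baseline weight and a baseline BMI of 22.

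- Arm A: 7 lose 12%, 1 gains 12%, and 28 gain 72/28 = 2.57%.
- Arm B: the mirror image.

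| Output | Arm A | Arm B |
|---|---|---|
| Mean | (−84 + 12 + 72)/36 = 0 | 0 |
| SD | √[(8 × 144 + 28 × 2.57²)/35] = 6.2 points | 6.2 points |
| Minimum, maximum | −12%, +12% | −12%, +12% |
| Bands <5 / 5–10 / >10 | 28 / 0 / 8 | 28 / 0 / 8 |
| BMI class changes | none | none |
| Median | +2.57% | −2.57% |
| Lost more than 10% | 7/36 = 19% | 1/36 = 3% |

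Nobody changes BMI class because 22 × 0.88 = 19.36 and 22 × 1.12 = 24.64 both lie in 18.5 to below 25. With equal baseline weights, the kg statistics match in the same way as the percentages. Only the median differs, and it is positive in the arm with the larger number of substantial losses.

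**The case against.** The strongest reply is that the endpoint already shows direction. The kg change keeps its sign and comes with a median, minimum and maximum. The SAP sentence can be read as presenting that kg change within each band, in which case a >10% band made up of losses would show negative values. The SAP overrides the protocol (Protocol 12.1). Unsigned bands also have a plausible purpose: a first band below 5% matches the two-sided stability range in inclusion criterion 6. Fluid overload has its own adverse-event query (SAP 7.2, Table 8) with risk differences, and SAP 3.5 plots urine volume, oral intake and parenteral support volume. The endpoint is untested, and signed counts can be derived from the same data at reporting.

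Most of this stands, and it rules out two stronger readings. First, a reader might infer that the plan cannot tell weight loss from weight gain. It can, in part. If 4 of 36 active patients lost more than 10% and 4 of 36 placebo patients gained more than 10%, a count by band would show 11.1% in both arms, but the kg extremes would reveal the difference and the arm means would be pushed apart. Second, a reader might infer that the bands hide whether reduced support leads to weight loss or to fluid gain. No weight-band table could show that, because weight is not cross-classified by change in support or by oedema.

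What the reply does not supply is the count itself. Minimum and maximum each describe one patient, kg is not percent, and the wording does not settle whether counts or kg statistics are shown. A fully signed reading is strained, but it would put every loss in the lowest band, which also needs ruling out.

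**Conclusion.** The point holds in a narrow form. The bands in both documents are unsigned and, on the plain reading, pool losses with gains. No planned summary gives the number of patients per arm losing 5–10% or more than 10% apart from those gaining as much. The constructed example shows that a 7 versus 1 imbalance in large losses can leave every planned weight output except the median unchanged. It rests on chosen values and an exact mirror image, so it shows that this is possible and says nothing about how likely it is.

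The consequence is small. The table is descriptive, and no test, error rate or confirmatory conclusion depends on it. The documents do not support saying that direction is lost from the endpoint, or that this table was ever able to attribute a weight change to reduced support or to fluid.

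**What to change.** In SAP 3.4, replace the three bands with five signed bands of percentage change in body weight from baseline to Week 24:

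- loss greater than 10%
- loss of 5% to 10%
- within ±5%
- gain of 5% to 10%
- gain greater than 10%

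State the boundary handling. Keeping the present convention would put exactly 5% and exactly 10% in the 5–10% bands. State that the table shows n and % of patients by treatment group, with the number of patients with a Week 24 weight as denominator. Keep the kg summary and the BMI shift table as they are. Do not present the new table as evidence about the cause of a weight change.

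The cost is a line or two of SAP text and a small change to one table program. Baseline and Week 24 weights are already collected.
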